8.7. ASSESSMENT TIME WINDOWS

The Baseline visit should occur within 28 days of the screening visit. For all scheduled visits, allowable visit windows and study procedures are \pm 14 days from the calculated target day. The target day is defined as (Baseline Visit + 75 days) for the Day 75 target day, and (Baseline Visit + 365 days) for the Day 365 target day. If multiple measurements occur within the assessment time window, the measurement closest to the scheduled target day will be analyzed. Data collected outside of the specified time window will not be included in the primary analysis.

8.8. DESCRIPTIVE ANALYSES

Characteristics of studied patients (i.e., demographics, disease status, glucose & hba1c levels) and measures of study feasibility (i.e., enrollment refusal rate, proportion of enrolled subjects who are successfully transplanted) will be summarized using descriptive statistics (i.e., means, standard deviations, medians, percentages) and 2-sided 95% confidence intervals.

8.9. EFFICACY ANALYSES

The primary efficacy analyses will involve the use a general linear mixed model (GLMM) to test whether the primary endpoints differ over time between subjects assigned to the AAT arm when compared to subjects assigned to placebo. The analysis will be performed on the mITT and PP populations, although the analyses within the mITT population will be considered primary.

Contrasts will be constructed to estimate the AAT treatment effect on outcomes at day 75 and at day 365. To account for the fact that observations within the same subjects will be correlated, various error covariance structures will be considered, including unstructured, autoregressive, and compound symmetry. If model assumptions are not met (e.g. normality) alternative strategies will be utilized, including transformations of dependent variables and non-parametric alternatives. Any pre-transplantation subject characteristics be found to be significantly different between the study subjects and historical controls will be included as covariates for all between-group comparisons. Model fit will be assessed using criteria such as Akaike Information Criterion. All primary and secondary outcomes will be reported in study communications.

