3.5.3. Exploratory endpoints

- Measurements of primary and secondary endpoints at day 75±14.
- Time course of instant blood mediated inflammatory reaction as measured by thrombin-anti-thrombin (TAT), C5a and c-peptide levels before, in the middle and after initiation of islet infusion, and 3h post islet infusion.
- Time course of inflammatory chemokines/cytokines as assessed by serum level of CXCL8, CCL2 (MCP-1), CCL3, CCL4, CXCL10 (IP-10), CXCL9 (MIG), IL-6, IL-10, INF- γ , TNF- α , and IL-1 β [pre-infusion, and 24, 72 and 168hrs, and day 14, and 21 after the end of islet infusion].
- Basal to 240 min time course of glucose, and C-peptide derived from the MMTT (day 75±14 to day 365±14).
- The proportion of patients with an HbA1c \leq 6.5% (day 365±14 days post-transplant only)
- Cumulative number of severe hypoglycemia events.
- The proportion of patients with an HbA1c \leq 6.5% at day 365±14 AND are free of severe hypoglycemic events from day 75±14 to day 365±14 inclusive.
- Daily oral Morphine Equivalents on day prior to visit (day 75±14 to day 365±14).
- Proportion of patients remaining on narcotics (day 75±14 to day 365±14).
- RNA expression profile in peripheral blood mononuclear cells (PBMCs) at 168 h post transplantation. RNA analysis will be done in at least 10 patients to guarantee post-treatment sampling in at least 3-4 patients randomized to AAT and 3-4 to control.
- SF-12 Quality of Life score

3.5.4. Safety endpoints:

- Incidence and severity of Adverse Events and Serious Adverse Events
- Standard laboratory tests including hematology (hematocrit, hemoglobin, red blood cells, platelets, white blood cells, differential white blood cell count), clinical chemistry (sodium, potassium, serum creatinine, blood urea nitrogen, total bilirubin, alanine aminotransferase (ALT), aspartate aminotransferase (AST) and coagulation (International Normalized Ratio (INR), partial thromboplastin time (PTT)), at pre-transplant hospital admission and post-transplant hospital

discharge].

- Vital signs, i.e. blood pressure (BP) and heart rate (HR) at pre-transplant hospital admission and post-transplant hospital discharge. ALT/AST, INR/PTT
- Weight loss from pre-transplant value [time frame: day 75±14 and 365±14 after the transplant]
- Serum level of albumin and pre-albumin (absolute and change from pre-transplant value) [time frame: day 75±14 and 365±14 after the transplant].

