6.1.2 Infusion of the Investigational Product

Infusion of AAT will start on the day of islet transplantation before anesthesia and pancreatectomy, which is approximately 6-8 hours before islet infusion. The clinical PIs, Drs. [name] and [name], will identify the time to start the study drug infusion. Starting and ending time of drug administration, amount of drug infused, and infusion rate will be recorded for each subject. On Average, TP-IAT patients stay in the hospital for 7-28 days after islet transplantation. If they stay till 21 days post transplantation, they can have all four AAT injections in the hospital. If they are discharged earlier, patients will be requested to return to MUSC for additional drug infusion(s). A nurse will administer the AAT or placebo infusion to the patient while in the hospital. A nurse in the GI surgery clinic or SCTR outpatient clinic will administer AAT or placebo to patients discharged but returning for one of the weekly visits. The nurses infusing these drugs will be trained on the day of administration concerning the few known side effects of AAT and rate of infusion.

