6.3. POST-OPERATIVE ASSESSMENTS

All routine measurements for TP-IAT patients will be measured according to current protocols for this patient population. SF-12 Quality of life and reduction in narcotic dose of morphine or equivalent will be obtained from the Islet Longitudinal Outcome Database (ILOD) which has granted this project authorization to use their information. . The following will be assessed during hospital stay and each time or when patients return for drug injection:

6.3.1. Instant blood mediated inflammatory reaction (IBMIR): 3ml of blood will be collected before AAT injection, before, in the middle, and after initiation of islet infusion and 3h post islet infusion. Serum will be collected and stored in -70 ° C for analysis of thrombin-anti-thrombin complex (TAT), C5a, and c-peptide level.

6.3.2. Chemokines/cytokines: A blood sample will be obtained at 0, 24, 72, and 168 h (before AAT injection), and day 14 (before AAT injection), and 21 (before AAT injection) post transplantation to measure chemokine and cytokine expression in the serum using the Lumix machine. Each time 5 ml of blood will be collected and centrifuged; aliquots of serum will be stored in in -70 ° C for further analysis.

6.3.3. DNA testing: A 10 ml whole blood sample will be collected during screening, and stored in -70 °C for isolation of genomic DNA for further analysis. This future analysis may be conducted by the PI or by other researchers who obtain IRB approval for their research. This research may involve genetic studies. The specimens will be labeled with a code that only study personnel can link back to the patient. Researchers outside of this study will not be given a link between the code number and patient's name or any other identifying information. We expect to store the specimens long-term for future studies on disease condition. Participant will not be contacted for additional consent. The investigators will not tell patient what they find out about the patient, nor will contact the patient if a test becomes available to diagnose a condition that a patient might have or later develop. Results will not be placed in the individual participant's medical record.

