8.3. SAMPLE SIZE JUSTIFICATION

We recognize that the number of participants is small given the heterogeneity of chronic pancreatitis but believe the numbers are appropriate for a proof-of-concept translational study. The goal of this aim would be to test whether IAT + AAT is feasible in this patient population and to obtain preliminary assessments of its success. Having n=32 subjects treated with AAT

(and n=16 placebo controls) would allow us to make relatively precise estimates of feasibility measures and means of the study outcomes, with 95% confidence intervals that would extend approximately 0.3 standard deviation units in either direction. While recognizing that the standard deviation will be slightly higher in the control population, we recognize that all hypothesis testing will be considered exploratory, enabling 80% power to detect moderately large differences (effect sizes of 0.9 standard deviation units) between the AAT and treated control groups with respect to the study outcomes, including the 4 hour C-peptide level AUC obtained at 12 months, assuming up to a 10% loss to follow-up over the 12 months. Having these numbers of subjects would also allow us to make preliminary comparisons between outcomes in the IAT + AAT group and outcomes observed in a group of 150 historical controls, each of whom received a total pancreatectomy with IAT at MUSC from 2009-2015. Most importantly, the data (e.g. means, standard deviations, and effect size estimates) from 32 subjects receiving AAT treatment, 16 control subjects receiving islets alone, and 150 historical controls will be vital for use in designing a larger more definitive randomized controlled trial in the future. Using 2:1 randomization will help provide more precise estimates of outcomes in the IAT + ATT group and may also help with study recruitment, as subjects may tend to be more willing to consent if they have a stronger probability of receiving the active experimental treatment.

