8.4. RANDOMIZATION

A randomization system will be developed by the biostatistician. The objective of randomization is to prevent possible selection bias by providing random treatment assignment to each subject; and to maintain treatment balance with respect to relevant prognostic variables.

Each cohort will start from a permuted block randomization with a block size of 6, including 4 assignments to the AAT arm and 2 assignments to the placebo arm. This initial block of 6 patients will provide information for early safety assessment of AAT.

Following the initial block, additional subjects will continue to be randomized between AAT and placebo in a 2:1 fashion, using random block sizes of 3 and 6.

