8.12. MECHANISTIC ANALYSIS

Since many of the mechanistic endpoints will be collected at multiple time points for each participant, statistical models appropriate for longitudinal data analyses will be used. For example, serum samples for cytokines will be collected at Baseline, day 1, 3, and 7 days post transplantation. The GLMM used to compare treatment groups will be of the form:

$$Kynurenine_{ij} = \alpha + \beta_1 \cdot Treatment_i + \beta_2 \cdot Kyn_0 + \beta_3 Week_j + \gamma_i + \gamma_{ij} \cdot Week_j + \epsilon_{ij}$$

This GLMM example treats cytokine as the dependent variable, including fixed effects for treatment group, baseline cytokine, and week, along with random subject intercepts (γ_i) and random subject slopes (γ_{ij}). Link functions appropriate for each dependent variable (i.e. each mechanistic outcome) will be selected, depending on its distributional form. Similar models will be constructed for other mechanistic endpoints.

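### Section 8.9, as written, lets a significance test against historical controls choose the covariates of the randomised AAT-versus-placebo model, so that model is not fixed in advance and prognosis plays no part in the choice

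*Combined protocol and SAP*

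**What the plan says.** Section 8.9 (Efficacy analyses) defines the primary analysis as a general linear mixed model comparing the AAT and placebo arms, with treatment contrasts at days 75 and 365. The same section then gives the only covariate rule for the efficacy models: pre-transplantation characteristics "found to be significantly different between the study subjects and historical controls will be included as covariates for all between-group comparisons". It gives no candidate list and no significance level for that test.

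Other sections bear on the point:

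- Section 8.3 plans "preliminary comparisons between outcomes in the IAT + AAT group and outcomes observed in a group of 150 historical controls", separately from the randomised comparison. It also says "all hypothesis testing will be considered exploratory, enabling 80% power to detect moderately large differences", at 0.9 SD with up to 10% loss to follow-up. It gives as the most important output the estimates needed to design a larger trial.
- Section 8.4 states as one aim of randomisation "to maintain treatment balance with respect to relevant prognostic variables". It names no such variables and describes no stratification.
- Section 8.6 mentions baseline covariates only for the imputation model of the sensitivity analysis.
- Section 8.12 does fix a covariate in advance for the mechanistic outcomes, "including fixed effects for treatment group, baseline cytokine, and week, along with random subject intercepts".

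**The concern.** AAT versus placebo is the between-group comparison that Section 8.9 defines, and no other section narrows the word *all*. A statistician who follows the text would compare the trial subjects with the historical cohort, keep whatever differs significantly, and put it into the randomised model.

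That test measures how the trial population differs from an earlier one. It does not measure whether a variable predicts C-peptide AUC. A strong predictor that matches the historical group is usually left out; a variable that has drifted is added even if it is unrelated to outcome. The covariate list stays unknown until the comparison has been run.

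Selection uses neither arm nor outcome, so the randomised contrast stays unbiased and its type I error is preserved. What is at stake is the precision of an effect estimate from at most 32 v 16 subjects, and whether the primary model can be reproduced from the plan alone.

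**Working it through.** **Inputs from the plan.** 32 AAT and 16 placebo (Section 3.1); effect 0.9 SD, 10% loss, 80% power, 150 historical controls (Section 8.3). Completers: 32 × 0.9 = 28.8 and 16 × 0.9 = 14.4, so N = 43.2. The level for the power figure is not stated; two-sided 5% is assumed, in line with the 95% intervals.

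**The plan's figure.** SE = √(1/28.8 + 1/14.4) = √0.10417 = 0.3227 SD. Then 0.9/0.3227 = 2.79, and Φ(2.79 − 1.96) = 79.6%. The stated 80% reproduces with a normal approximation and contains no covariate adjustment. With the noncentral t distribution it is 77.7%, the baseline used below.

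**What the selection test responds to.** For 48 v 150 at an assumed 5% level, a characteristic is selected with probability 5% at no shift, 22% at 0.2 SD, 44% at 0.3 SD and 85% at 0.5 SD, whatever its relation to outcome. With no true differences, at least one of ten independent characteristics enters with probability 1 − 0.95¹⁰ = 40%.

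**Closed-form power with k covariates explaining R² of the variance.** Var = (1 − R²)(1/28.8 + 1/14.4)(1 + k/(N − k − 3)), df = N − 2 − k, half-width = t(0.975, df) × SE. The documents give no R², so every value is assumed.

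- k = 0: df = 41.2, half-width 2.019 × 0.3227 = 0.65 SD, power 77.7%.
- k = 3, R² = 0: SE = 0.3227 × √(1 + 3/37.2) = 0.3355, half-width 2.024 × 0.3355 = 0.68 SD, power 74.4%.

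| Pre-specified covariates | R² 0 | 0.05 | 0.1 | 0.2 | 0.3 | Break-even R² |
|---|---|---|---|---|---|---|
| One | 76.7% | 78.7% | 80.9% | 85.2% | 89.5% | 0.026 |
| Two | 75.5% | 77.6% | 79.8% | 84.2% | 88.7% | 0.052 |

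Break-even is the R² at which power equals the unadjusted 77.7%.

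**Simulation of the rule.** 20,000 runs per scenario; 48 trial and 150 historical subjects; ten independent normal candidates, two of them prognostic with total R² 0.2; drift of 0.5 SD where present; t-test at 5%. Selected covariates enter a linear model fitted to 29 v 14 completers.

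| Which candidates drift | Unadjusted | Rule | Two prognostic pre-specified | Rule − unadjusted | Rule − pre-specified |
|---|---|---|---|---|---|
| None | 76.8% | 76.7% | 83.3% | −0.1 | −6.6 |
| Three non-prognostic | 77.0% | 74.1% | 83.7% | −2.9 | −9.6 |
| One prognostic, two not | 76.8% | 77.5% | 83.4% | +0.7 | −5.9 |
| Two prognostic, one not | 76.9% | 81.3% | 83.2% | +4.4 | −1.9 |
| Only the two prognostic | 77.5% | 82.6% | 83.8% | +5.1 | −1.2 |

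The mean estimate was 0.90 for a true 0.9 under all three approaches. Rejection at zero effect (unadjusted / rule / pre-specified) was 5.2 / 5.1 / 5.2% with three non-prognostic candidates drifting and 5.3 / 5.2 / 5.1% with only the prognostic ones drifting. The rule picked at least one prognostic covariate in about 10% of runs when neither drifted and in 98% when both did. Mean half-width under the rule was 0.61 to 0.68 SD, against 0.65 unadjusted and 0.60 pre-specified.

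**Link to the mixed model.** These are single-visit figures. With both visits observed, an unstructured covariance and visit-specific treatment and covariate terms, the day-365 contrast equals the single-visit analysis. One simulated data set gave an estimate of 1.0196 and SE 0.3547 both ways.

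**The case against.** The strongest reply is that the sentence was probably meant only for the historical comparison planned in Section 8.3, where adjusting for such differences is reasonable. That may well be so, but the text does not say it.

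Second, little harm is shown. There is no bias; in four of five scenarios the rule loses almost nothing against an unadjusted model or gains; all testing is labelled exploratory. The 1.2 to 9.6 point shortfall is measured against an adjusted model that the plan never promised, under assumed R² and drift. This stands as a description of size: it is a forgone gain, not a failure of the stated 80%. It does not defend the rule, because the plan's own main output is estimates for a later trial.

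Third, the contrast with Section 8.12 is imperfect. The mechanistic model adjusts for the baseline value of its own outcome, whereas the meal test is done only at days 75 and 365, so the primary endpoint has no baseline value. That stands. It rules out one kind of covariate, not the naming of another.

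Fourth, the rule is itself stated in advance, and Section 8.9 also leaves covariance structure, transformation and non-parametric alternatives open. Both are true. Only the resulting covariate list is open here, and fixing it would not by itself fix the whole model.

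**Conclusion.** The concern holds. As written, a test against historical controls selects the covariates of the randomised model without regard to prognosis, and the list cannot be known in advance. Validity is not affected. Under the assumed scenarios the rule changes power by −2.9 to +5.1 points relative to no adjustment, and the documents cannot settle which direction applies. In none of the scenarios did it reach the power of naming the prognostic covariates in advance. That last comparison assumes the named covariates really are prognostic; one that explains less than about 3% of the variance, or two that explain less than about 5%, would cost a little power. Given the exploratory status and the probable narrower intent, this should be fixed, but it does not threaten the trial. Confidence in its practical size is medium.

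**What to change.** 1. Confine the rule in Section 8.9 to comparisons with historical controls.
2. For AAT versus placebo, name before unblinding one or two pre-dose covariates that are already collected and expected to be prognostic, and keep them whatever any test shows; or state that the model has none.
   - *C-peptide before the first dose* is one candidate, once its timing is reconciled. Section 6.3.1 says "3ml of blood will be collected before AAT injection". Section 3.5.3 instead lists "C5a and c-peptide levels before, in the middle and after initiation of islet infusion, and 3h post islet infusion". The first dose is given "before anesthesia and pancreatectomy, which is approximately 6-8 hours before islet infusion" (Section 6.1.2), so a sample taken just before islet infusion is not a pre-dose value. The footnotes in Appendix 1 also start at islet infusion. The row's one unfootnoted mark falls under Screening in the extracted table, where columns may have shifted.
   - *Pre-transplant HbA1c* (Section 8.8) is the other, only if recorded for every subject. Section 6.1.1 does not list it as a required test and Appendix 1 has no row for it.
   - Body weight needs a specific reason, because the endpoint is already normalised by IEQ/kg and the meal is dosed per kg.
3. Secondary: Section 8.3 gives the procedure, centre and years of the 150 historical controls but no eligibility restriction. Apply Sections 4.1 and 4.2 to them before comparing, since adjustment cannot replace restriction for a characteristic that no trial subject has.

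Suggested text:

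> Characteristics that differ between study subjects and historical controls will be covariates only in comparisons with historical controls. The AAT-versus-placebo model will include [one or two named pre-dose variables, or none], fixed before unblinding and regardless of any test.

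The cost is SAP wording, one or two degrees of freedom, and either reconciling the C-peptide sample times or confirming that HbA1c is complete. Restricting the historical group may make it smaller.

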8.10. SAFETY ANALYSES

Study subjects will be asked to report any and all AEs/new symptoms at any time from study enrollment until 52 weeks after study treatment, whether or not they attribute them to the study intervention or procedures. Subjects, who discontinue the study treatment regimen for any reason, including subjects who are treatment failures due to unable to return for some of the treatment injection(s) will be encouraged to attend the remaining visits for assessment of safety, secondary and pharmacokinetic endpoints.

To assess safety in this population, vital signs will be performed at each of the study visits. Additionally, medical history will be collected at screening and baseline and adverse events occurring after start of study therapy will be recorded.

Since the safety endpoints are primarily binary indicators for each subject (e.g. experiencing a particular AE during the 24-weeks post-treatment), their analyses will involve logistic regression models. For certain safety endpoints, it may be more appropriate for them to be analyzed using survival techniques, which are more suitable for time-to-event data than logistic regression. In such circumstances, Cox proportional hazards models will be used to compare treatment arms; however, should the proportionality assumptions not hold, alternative strategies (e.g. stratified analyses) will be used. The safety analyses will be conducted in the Safety Population.

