2.4.2. Benefits to society

This study may identify a useful medication that will benefit patients with islet transplantation.

3. OVERALL STUDY DESIGN AND PLAN DESCRIPTION:

3.1. STUDY DESIGN:

Experimental design: We propose to enroll a total of 48 CP patients who are scheduled for TP-IAT. This will be a 2:1 randomized, double blind, controlled study in which 32 patients receive islet cell transplantation together with intravenous AAT 60 mg/kg/week for 4 weeks, and 16 patients receive islets with intravenous 0.9% saline control in equivalent volume.

CP patients planning TP-IAT will receive an IRB approved consent form that describes the research study. Following signed consent, they will be enrolled and receive a baseline study visit. On the day of TP-IAT, an intravenous injection of AAT at the FDA approved dose of 60mg/kg or 0.9% normal saline will be infused before surgery. The autologous islet transplantation procedures will remain as routinely performed at MUSC. On the day of transplantation, the pancreas will be harvested and transferred to the Center for Cellular Therapy (CCT). Islets will be isolated and transplanted back to the patient via portal vein infusion. AAT or placebo will be given on day 0, 7, 14 and 21 days of islet transplantation.

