- Proportion of patients falling into one of the following levels of steatorrhea severity [time frame: day 75±14 and 365±14 after the transplant];
 1. No steatorrhea;
 2. Steatorrhea few times per week;
 3. Steatorrhea daily;
 4. Stool incontinence.
- Proportion of patients falling into one of the following malnutrition risk levels (poor prognosis, significant risk, increased risk, normal) according to pre-albumin level [time frame: day 75±14 and 365±14 after the transplant].
- Cumulative number of episodes of documented hypoglycemia (documented symptomatic; asymptomatic) [time frame: from day 75±14 to day 365±14 after the transplant].
- Cumulative number of diabetic ketoacidosis-related events [time frame: from day 75±14 to day 365±14 after the transplant].

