6.3.6. Mixed meal tolerance test (MMTT)

MMTT tests will be performed at 75±14 and 365±14 days post-surgery. During the MMTT, patients will be asked to drink a special drink called 'BOOST', which will be given at a dose of 6 mL per kilogram body weight and contains a mixture of protein, fat and carbohydrates. Patient's blood will be drawn at 0, 15, 30, 60, 90, 120, 180 and 240 min after drinking the boost. In each time point, 4ml of blood will be collected, 2ml for measuring blood glucose, and 2ml to measure c-peptide levels. Samples will be sent to the blood lab for analysis.

6.3.7. Safety laboratory tests:

Laboratory tests will be performed before hospital discharge. These are standard of care tests done in all TP-IAT patients.

6.3.6. Vital signs: Blood pressure and heart rate will be measured before hospital discharge.

6.4. FOLLOW-UP VISITS:

Autologous islet transplant recipients will be followed up life-long in our center. For this study specifically, patients will be followed up till 12 months post-transplantation. They will have to attend 2 follow-up visits scheduled on day 75 ± 14 and 365 ± 14 days after the transplant, this can be combined with their routine returning visits.

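### Section 8.10 gives 24 weeks as its only window for the binary adverse-event indicator, but adverse events are collected to 52 weeks and recorded through day 365

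*Combined protocol and SAP*

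**What the plan says.** The combined protocol and SAP sets adverse-event timing in several places.

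- **Collection, section 8.10, first paragraph:** subjects report events "at any time from study enrollment until 52 weeks after study treatment".
- **Analysis, section 8.10, third paragraph:** safety endpoints are described as mainly binary per-subject indicators analysed by logistic regression. The example in parentheses is "experiencing a particular AE during the 24-weeks post-treatment". Cox models are allowed for some endpoints, with no censoring time given.
- **Endpoint, section 3.5.4:** "Incidence and severity of Adverse Events and Serious Adverse Events", with no time frame.
- **Other safety endpoints, section 3.5.4:** several have their own time frame, for example "Cumulative number of diabetic ketoacidosis-related events [time frame: from day 75±14 to day 365±14 after the transplant".
- **Follow-up, section 6.4:** "patients will be followed up till 12 months post-transplantation", and "They will have to attend 2 follow-up visits scheduled on day 75 ± 14 and 365 ± 14 days after the transplant".
- **Schedule, Appendix 1:** adverse events are recorded from baseline through D365.
- **Dosing, section 3.1:** "AAT or placebo will be given on day 0, 7, 14 and 21 days of islet transplantation".

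**The concern.** The collection period and the analysis example stand in the same section and cannot both define the adverse-event window. A binary indicator has no meaning without its window, because the window decides whether each patient is a 0 or a 1. If the 24-week text is followed, a patient whose first event comes later enters the model as event-free although the trial holds a record of the event. If it is not followed, the plan states no analysis window for the indicator, and one could be chosen after the data are seen.

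Safety is half of the objective in section 3.4, and the arms are small. With 32 AAT and 16 placebo patients, reclassifying one patient moves an event proportion by 1/32 = 3.1 percentage points or 1/16 = 6.25 percentage points.

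**Working it through.** The plan gives no figure for this point that could be reproduced. Its only power statement (section 8.3) concerns a 0.9 SD difference and does not enter here. The check is day arithmetic, followed by a sensitivity calculation on assumed event patterns.

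**Inputs.** First infusion day 0 and last infusion day 21 (section 3.1). Analysis example 24 weeks = 24 × 7 = 168 days, and collection 52 weeks = 52 × 7 = 364 days (section 8.10). Final visit day 365, with a window of ±14 days (section 6.4) or ±15 days (Appendix 1).

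**Step 1: does anything else in the trial sit at 24 weeks?** The day-75 visit can fall as late as 75 + 14 = day 89, and the day-365 visit as early as 365 − 14 = day 351. No study visit lies between them. No other section mentions 24 weeks.

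**Step 2: follow-up time after the window.** The plan does not say when the post-treatment clock starts, so both ends of dosing are tried.

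| Clock starts | Window ends | Days left to day 365 | Share of 365 days |
|---|---|---|---|
| First infusion, day 0 | 0 + 168 = day 168 | 365 − 168 = 197 | 197/365 = 54.0% |
| Last infusion, day 21 | 21 + 168 = day 189 | 365 − 189 = 176 | 176/365 = 48.2% |

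Comparing 24 with 52 weeks on one clock gives 1 − 24/52 = 53.8%, inside the same range.

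**Step 3: time is not events.** The documents give no adverse-event rates, so both patterns below are assumptions.

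- *Constant hazard.* With 12-month risk p and a window ending on day w, the risk inside the window is 1 − (1 − p)^(w/365). For p = 30% this is 15.1% (w = 168) or 16.9% (w = 189). For p = 50% it is 27.3% or 30.2%.
- *Events clustered around surgery.* Let a share f of first events fall in the first 30 days and the rest be uniform over the remaining 335 days. The share after the window is (1 − f) × (365 − w)/335. For f = 0.5 this is 0.5 × 197/335 = 29.4% or 0.5 × 176/335 = 26.3%. For f = 0.9 it is 0.1 × 197/335 = 5.9% or 0.1 × 176/335 = 5.3%.

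So the share of first events lost could be near half under a constant hazard, or about 5% to 29% under clustering.

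**Step 4: the 52-week collection period.** From the first infusion it ends on day 364, which agrees with the day-365 visit. From the last infusion it ends on day 21 + 364 = day 385, after the latest final visit (day 379 with ±14, day 380 with ±15). Whether collection agrees with Appendix 1 therefore depends on an anchor the plan does not state.

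**The case against.** The strongest reply is that the 24 weeks appear only in an example explaining why logistic regression suits binary data. The endpoint itself, in section 3.5.4, has no such limit. The phrase may be carried over from another plan. Section 8.12 likewise writes its example model for kynurenine, which is not a listed endpoint, although carry-over is only an inference. This reply stands to the extent that the plan does not firmly restrict the endpoint to 24 weeks. It does not remove the contradiction, because the example holds the only analysis window stated for the indicator.

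A reader might also draw stronger conclusions that the documents do not support:

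- **That the whole safety comparison loses half the follow-up.** Weight, albumin and pre-albumin, steatorrhea and malnutrition risk are assessed at days 75 and 365. Documented hypoglycemia and ketoacidosis are counted from day 75 to day 365. An example in section 8.10 does not override these.
- **That reactions during dosing are excluded.** Taken literally, post-treatment could start after day 21. But section 8.10 also records events from the start of study therapy, Appendix 1 records them from baseline, and no text removes days 0 to 21 from the analysis.
- **That late events rest on many months of recall at day 365.** Subjects may report at any time, section 7.2 requires expedited reporting of serious events, and section 7.3 provides quarterly reports to the monitoring committee.
- **That 52-week collection necessarily outruns the last visit.** This is true only if the clock starts at the last infusion.

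**Conclusion.** Section 8.10 contradicts itself on the adverse-event window and needs correcting. If the 24-week example is applied, first events after about day 168 or day 189 count as non-events in the logistic comparison of the arms, which leaves out 48% to 54% of follow-up time. That range rests only on the dosing days, the day-365 visit and the choice of anchor.

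It should not be read as half of the events. No event rates are given, and with four infusions around major surgery the loss could be far smaller. The point concerns binary adverse-event indicators that have no time frame of their own. It does not reach endpoints already framed to day 365. All hypothesis testing is declared exploratory (section 8.3), which limits the consequence but does not settle which window applies.

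**What to change.** In section 8.10, replace the 24-week phrase with the full adverse-event follow-up, from the start of study therapy through the day-365 visit. For any Safety Population subject who was not infused, start the window on the day of surgery, because section 8.2.3 requires only consent and surgery.

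State the anchor of the 52-week collection period so that it agrees with Appendix 1. Counting from the first infusion gives day 364 and does agree. Counting from the last gives day 385, and Appendix 1 would then have to show how events after the final visit are captured.

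If a 24-week window is intended, give its anchor and rationale and report it alongside the full-follow-up analysis.

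The cost is wording. The analysis change uses events already collected through day 365. Because the SAP is part of the protocol, the revised text would go to the IRB as an amendment under section 10.
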